The assessment of the relationship of an AE to the administration of IMP is a clinical decision based on all available information at the time of and after the occurrence of the event. The factors which may be considered when evaluating the relationship of an AE to the IMP include: time from exposure to IMP until onset of the event; recovery or improvement on discontinuation of IMP; availability of alternative explanations such as underlying or intercurrent diseases; concomitant medications or treatments; pharmacology of the IMPs; known response pattern for this class of drug; recurrence on reintroduction of the IMP.

If there is no reasonable possibility for suggesting a relationship, then the AE should be classified as ‘not related’. The adverse event should be classified as related if a reasonable possibility of a causal relationship between the event and IMP exists. This means that there are facts (evidence) or arguments to suggest a causal relationship. The causality must be documented in the source document and eCRF.

The following additional guidance may be helpful:

Term	Relationship	Definition
Related – Reasonable possibility	Yes	The temporal relationship between the event and the administration of the IMP is compelling and/or follows a known or suspected response pattern to that product, and the event cannot be explained by the patient’s medical condition, other therapies, or accident.
Not Related – No reasonable possibility	No	The event can be readily explained by other factors such as the patient’s underlying medical condition, concomitant therapy, or accident and no plausible temporal or biologic relationship exists between the IMP and the event.

8.5.2.2.13.1.3 Outcome Categorization

The outcome of AEs must be recorded during the course of the clinical trial in the eCRF. Outcomes are as follows:

- Recovered/Resolved
- Recovering/Resolving
- Not recovered/Not resolved/ongoing
- Recovered/Resolved with sequelae
- Fatal
- Unknown

8.5.2.2.13.1.4 Clinical Laboratory Evaluations

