The onset date of the SAE is defined as the date the event meets serious criteria. The stop date is the date the event no longer meets serious criteria, the date the symptoms resolve, or the event is considered chronic. In the case of hospitalizations, the hospital admission and discharge dates are considered the onset and SAE resolution dates, respectively.

8.5.2.2.13.2.5 Fatal Outcome

Any SAE that results in the patient's death (i.e. the SAE was noted as the primary cause of death) should have Outcome „Fatal” and the date of death recorded as the stop date of the SAE.

For all other events ongoing at time of death that did not contribute to the patient's death, the outcome should be considered unknown, with the SAE stop date (date of death) recorded.

For any SAE that results in the patient's death or any ongoing events at the time of death, the action taken with the IMP should be recorded as “dose not changed” or “not applicable” (if the patient never received IMP).

8.5.2.2.13.2.6 Regulatory Agency, Ethics Committee, and Investigative Site Reporting

The Sponsor is responsible for Suspected Unexpected Serious Adverse Reaction (SUSAR) reporting to the relevant Regulatory Authorities/European Union (EU), central Ethics Committees and investigators participating in the clinical trial in compliance with the legal reporting obligations.

The expedited reporting will occur not later than 15 days after the Sponsor has first knowledge of the adverse reactions. For fatal or life-threatening cases the term will be maximal 7 days for a preliminary report with another 8 days for completion of the report.

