4.5 Safety Analysis

Adverse events (AEs) and serious adverse events (SAEs)

AEs will be coded by using the Medical dictionary for regulatory activities (MedDRA) version 23.0.

A treatment emergent adverse event (TEAE) is defined as an AE with AE onset date \geq date of first study medication. If a date is unknown or incomplete and the AE cannot definitely be considered as started before date of first study medication, the AE will be considered as TEAE, unless the AE resolution date is before the date of first study medication.

An AE overview table will be prepared showing the number of patients with at least 1 AE and at least 1 TEAE, TEAEs related to IMP, TEAEs related to IMP procedure (infusion), serious TEAEs, serious TEAEs related to IMP and serious TEAEs related to IMP procedure (infusion) as well as the total number of events in each category.

TEAEs as well as serious TEAEs will be tabulated by system organ class and preferred term (MedDRA). The number of events, as well as the number and rate of affected patients will be reported for each treatment group. Additional tables will be provided for TEAEs (system organ class and preferred term) summarized by severity, by relationship to IMP and by relationship to IMP procedure (infusion).

AEs that occur with AE onset date < date of first study medication are defined as “pre-treatment” events. All AEs for patients without treatment will be considered as pre-treatment AEs. Pre-treatment AEs will be listed only.

Individual patient data listings will be provided for all SAEs as well as additionally for all deaths only (AEs with outcome ‘Fatal’), unexpected adverse drug reactions as confirmed by the sponsor’s drug safety manager (AEs of patients with primary reason for discontinuation ‘Occurrence of a severe adverse reaction (SAR)’), discontinuation of IMP due to AEs (AEs with action taken regarding IMP ‘Drug interrupted’ or ‘Drug withdrawn’), or premature trial termination due to AEs (AEs of patients with primary reason for discontinuation ‘Adverse events necessitating withdrawal from the clinical trial’).

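### The relatedness guidance table contradicts the protocol's own reasonable-possibility rule and leaves events with both a plausible drug link and another explanation in neither category

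*Protocol*

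**What the plan says.** Protocol Section 8.5.2.2.13.1.2 (Relationship Categorization) handles relatedness in two layers.

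The running text gives a complete binary rule. Without a reasonable possibility of a link, the event is not related. Otherwise: "The adverse event should be classified as related if a reasonable possibility of a causal relationship between the event and IMP exists". The text explains this as the existence of facts or arguments pointing to a causal link. Among the factors an assessor may consider is the "availability of alternative explanations such as underlying or intercurrent diseases".

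A two-row table follows, introduced by "The following additional guidance may be helpful". Its Related row carries the reasonable-possibility label and requires that the temporal relationship "is compelling and/or follows a known or suspected response pattern to that product, and the event cannot be explained by" the patient's condition, other therapies or accident. Its Not Related row requires that other factors readily account for the event "and no plausible temporal or biologic relationship exists between the IMP and the event".

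SAP Section 4.5 uses the resulting field. The overview table counts related and serious related treatment-emergent events, and further tables are "summarized by severity, by relationship to IMP and by relationship to IMP procedure (infusion"). On expedited reporting, protocol Section 8.5.2.2.13.2.6 states: "The Sponsor is responsible for Suspected Unexpected Serious Adverse Reaction (SUSAR) reporting". It does not say whose causality judgement decides.

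**The concern.** One label carries two tests. Under the running text, another possible cause is weighed against the evidence for the drug. Under the Related row, another possible cause is enough to block the category. An investigator who follows the row and one who follows the text can classify the same event differently, and about 40 sites are planned.

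The related-event tables are not the only use of the field:

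- Protocol Section 10 lists serious adverse event data by severity and causality among the material for the DSMB.
- Section 8.5.2.2.13.1 asks for reporting after the end of the trial only for serious events considered related. There, relatedness is the gate.
- A SUSAR is by definition a suspected reaction, so a causality judgement feeds that decision too.

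If attribution is pulled down or varies by site, each of these uses inherits the problem.

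**Working it through.** The plan gives no figure to reproduce. The check sets the rule and the table side by side and goes through the possible cases.

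**Step 1: the attributes.** The two table rows use different thresholds for the link (compelling or matching a response pattern; no plausible relationship) and for the alternative explanation (cannot be explained otherwise; readily explained). That gives three levels of each, so 3 × 3 = 9 combinations. Assumption: a reasonable possibility means at least a plausible link.

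| Drug link | Other explanation | Running text | Table |
|---|---|---|---|
| None plausible | None | Not related | Neither |
| None plausible | Possible | Not related | Neither |
| None plausible | Ready | Not related | Not related |
| Plausible | None | Related | Neither |
| Plausible | Possible | Related | Neither |
| Plausible | Ready | Related | Neither |
| Compelling or pattern | None | Related | Related |
| Compelling or pattern | Possible | Related | Neither |
| Compelling or pattern | Ready | Related | Neither |

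**Step 2: the counts.** The table assigns 1 combination to Related and 1 to Not Related, leaving 9 − 1 − 1 = 7 in neither. The running text calls 2 × 3 = 6 related. Of those 6, the table confirms 1, leaves 5 unclassified and calls 0 not related.

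**Step 3: sensitivity to the assumption.** Suppose a reasonable possibility is read strictly, as a compelling link or response pattern only. The text then calls 1 × 3 = 3 combinations related; the table confirms 1 and leaves 2 unclassified. With both attributes collapsed to yes/no there are 4 cells, of which the table assigns 2. The cell with a plausible link and another explanation is again unassigned. The gap survives each reading. These are counts of wording combinations, not of events.

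**Step 4: is the unclassified case foreseeable here?** SAP Section 4.5 names multi-organ failure, hypersensitivity, adverse hemodynamic effects and cardiovascular effects as important risks. Protocol Section 8.4.5 says the virus itself may lead to multi-organ failure, and Section 6.7 raises direct cardiac involvement by the virus. Section 8.1 allows background standard of care, possibly including remdesivir. For several of the named risks, then, the protocol itself supplies another explanation. Section 6.7 also reports one fatal acute renal failure judged related in the earlier ARDS study. That study's causality criteria are not given, but an event of that kind in a critically ill patient could have difficulty meeting the Related row.

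**Step 5: what depends on the field and what does not.** Dependent: the related-event tables, the DSMB causality data, post-trial reporting of related serious events, and causality input to SUSAR assessment. Independent: tables of all treatment-emergent and all serious treatment-emergent events by arm, the important-risk tables by arm (both SAP Section 4.5), and reporting of every serious event to the sponsor within 24 hours (protocol Sections 8.5.2.2.13.2.1 and 8.5.2.2.13.2.2).

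**The case against.** The strongest reply is that the running text is already a complete rule, that it gives the overlap event a category, and that the table is offered only as helpful guidance. Nothing says the table replaces the rule. This is right about the table's status and is why the point is an internal inconsistency rather than two definitions of equal standing. It does not remove the problem: guidance that contradicts its own rule, under the same label, invites different classification, and the protocol does not say which governs.

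A reader might infer that the table pushes overlap events into Not Related. It does not. The Not Related row also needs the absence of any plausible link, so these events fall in a gap and the choice is left to the assessor.

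A reader might also infer that almost nothing would be called related, so that the related-event tables and SUSAR screening would be emptied. The documents give no event frequencies to support that, and a reaction with compelling timing and no other explanation still meets the Related row.

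Several safeguards stand. Assessment is double-blind and placebo-controlled, a designated physician classifies causality for all adverse events (protocol Section 8.5.2.2.13), adverse events are not tested statistically (Section 8.7.1.2.7), and the comparison of all events by arm does not use this field. They limit the damage but do not protect the four uses that depend on relatedness.

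**Conclusion.** The point holds as an internal inconsistency in protocol Section 8.5.2.2.13.1.2. The Related row adds a veto that the stated rule does not contain, and the two rows together are not exhaustive. Taking a reasonable possibility as at least a plausible link, the table confirms 1 of the 6 combinations that the rule calls related and leaves the other 5 unclassified.

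Related-event counts, DSMB causality data, post-trial reporting of related serious events and causality input to SUSAR assessment may be understated or vary by site. The share of events affected is unknown and could run from few to most. That the overlap is foreseeable rests on the risks and disease effects the documents name, not on observed frequencies. The between-arm safety comparison on all events, and the flow of serious events to the sponsor during the trial, are intact. The correction is worth making, but this is not a threat to the trial's main conclusions.

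**What to change.** - Delete from the Related row the condition that the event must have no other explanation.
- Reword both rows so that they are exhaustive and mirror the running text. Related: a reasonable possibility, with facts or arguments suggesting a causal link, where other explanations are weighed but are not a veto. Not related: no reasonable possibility.
- State that the running-text rule governs.
- Tell sites by memo, and bring any eCRF completion guidance into line.
- Before database lock, have the causality of serious events already assessed under the table checked, blinded to treatment.

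A broader change, calling every doubtful case or any event with plausible timing related, is not recommended. Under twice-daily dosing for seven days it could make many events in both arms related on timing alone, and it would drop a factor that the protocol asks assessors to weigh.

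The cost is a wording change, a memo and a limited query round. Somewhat more events may be called related in both arms.

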6.7 Risk-Benefit Considerations

Based on available information and the design of the clinical trial, the Sponsor considers the trial to be ethically acceptable.

In general, the adverse events in the first in human (FIH) Study (APN01-1-01) occurred with similar frequency between active and placebo treated subjects, without apparent dose-relatedness. In the Phase I-Study 204987 (Effects on the Response to Acute Hypoxia and Exercise) of APN01 with healthy subjects there were no serious adverse events, deaths or other significant adverse events. In the Phase Ib Study 204696 in patients with PAH, there were no SAEs associated with the infusion of GSK2586881 (APN01) or reported within the 2-week period of study observation [6].

In the ongoing open-labeled Phase II a-206246-Study with Patients with PAH there were no SAEs and no anti-ACE2 binding antibodies detected.

The hypernatremia reported with GSK258688 (APN01) in the Phase IIa-ACE114622-Study with patients with acute respiratory distress syndrome was mild and consistent with sodium levels in the placebo group, and a number of events occurred after discontinuation of drug. The episodes of pneumonia in subjects receiving GSK2586881 (APN01) in the same study were all considered nosocomial in origin and occurred between 5-36 days after the last dose of study drug.

During Part A of the Phase IIa-ACE114622-Study 3 subjects experienced a total of 9 SAEs that resulted in death, only one of which (acute renal failure), was considered to be related to study drug, and was reported 4 days after the last dose of study drug.

None of the fatal events in during Part B (3 fatal AEs - 2 in the placebo group due to multiple organ failure and septic shock and one in GSK2586881 (APN01) 0.4 mg/kg BID) was considered to be related to study treatment by the reporting investigator.

In general, the safety findings were consistent with a critically ill patient population with a wide range of underlying disease processes.

Fei Zhou et al. reported age, comorbidities, lymphocytopenia and elevated alanine aminotransferase, d-dimer, creatine kinase, high-sensitivity cardiac troponin I, prothrombin time, and disease severity to be associated with intensive care unit admission. In addition, angiotensin converting enzyme 2, the receptor for SARS-CoV-2, is expressed on myocytes and vascular endothelial cells, so there is at least theoretical potential possibility of direct cardiac involvement by the virus [7].

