8.5.2.2.13 Adverse and Serious Adverse Events Assessments

The investigator is responsible for ensuring that all adverse events observed by the investigator or reported by patient are properly captured in the patients' medical records.

Adverse events will be recorded in the AE page of the eCRF using a recognized medical term or diagnosis that accurately reflects the event.

All AEs will be reviewed, confirmed, and classified (causality and seriousness) by a qualified, designated physician.

Pre-existing conditions that are present at screening are not defined as adverse events. These should be documented as medical history. Nevertheless, an AE will be documented in case of a worsening of severity of a pre-existing condition. AEs reported between screening and IMP application are defined as pre-treatment AE.

8.5.2.2.13.1 Definition of Adverse Events, Period of Observation, Recording of Adverse Events

An **AE** is any untoward medical occurrence in a clinical investigation patient administered a pharmaceutical product and that does not necessarily have a causal relationship with this treatment. An AE can therefore be any unfavorable and unintended sign (including an abnormal laboratory finding), symptom, disease or exacerbation of a pre-existing condition temporally associated with the use of a medicinal (test) product, whether or not considered related to the medicinal product (ICH Guidance E2A 1995).

All AEs, including those associated with the IMP, are collected from the time of first dose administration, regardless of the relationship to the IMP. All AEs are to be recorded on the appropriate source documents and subsequently will be entered into the AE module of the eCRF. All AEs have to be recorded until the last trial day according to the clinical trial protocol. If the investigator becomes aware of a serious AE considered related to the IMP, it has to be reported ([contact]) even if it occurs after finalization of the clinical trial.

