A change in the value of a safety laboratory investigation can represent an AE if the change is clinically relevant or if, during treatment with the IMP, a shift of a parameter is observed from a normal value to an abnormal value, or a further worsening of an already abnormal value. When evaluating such changes, the extent of deviation from the reference range, the duration until return to the reference range, either while continuing treatment or after the end of treatment with the IMP, and the range of variation of the respective parameter within its reference range, must be taken into consideration.

If, at the end of the treatment phase, there are abnormal laboratory values which were not present at baseline, further clinical or laboratory investigations should be performed until the values return to within reference range or until a plausible explanation (e.g., concomitant disease) is found for the pathological laboratory values.

Changes in laboratory values that are clinically significant (cs) and are specific for COVID-19 do not need to be documented as adverse events (AE). Clinically significant changes in laboratory values that are not due to COVID-19 need to be documented as AEs.

The physician should decide, based on the above criteria and the clinical condition of a patient, whether a change in a laboratory parameter is clinically significant and therefore represents an AE.

8.5.2.2.13.1.5 Overdose and Medication Error

Overdose, or medication error (as defined below) must be reported to the Sponsor according to the SAE reporting procedure whether or not they result in an AE/SAE.

Overdose - Intentional or unintentional administration of a dose of study medication higher than the protocol prescribed dose for each patient.

Medication Error - A mistake made in administration, and/or use of the study medication. For studies, medication errors are reportable only as defined below.

Administration of an expired product should be considered as a reportable medication error when associated with an AE, or if otherwise appropriate.

Cases of patients missing doses of study medication are not considered reportable as medication errors.

8.5.2.2.13.2 Serious Adverse Event (SAE) Procedures

8.5.2.2.13.2.1 Reporting Procedures

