All initial SAE reports must be reported by the investigator to the Sponsor's Pharmacovigilance Department immediately, without undue delay, under no circumstances later than 24 hours following the first awareness of the event. All SAE follow-up reports must be reported in a timely manner. The investigator must complete, sign, and date the SAE form and verify the accuracy of the information recorded on the form with the corresponding source documents (Note: source documents are not to be sent unless requested) and e-mail the form to the Sponsor's Qualified Person for Pharmacovigilance:

Name: CTC North Safety Desk
[contact]
Email: [contact]

8.5.2.2.13.2.2 Serious Adverse Event Definition

A SAE is any untoward medical occurrence (whether considered to be related to IMP or not) that follows the first IMP administration at any dose:

- Results in death
- Is life-threatening

NOTE: The term 'life-threatening' in the definition of 'serious' refers to an event in which the patient was at risk of death at the time of the event; it does not refer to an event which hypothetically might have caused death if it was more severe.

- Requires inpatient hospitalization or prolongation of existing hospitalization
- Results in persistent or significant disability/incapacity
- Is a congenital abnormality/birth defect
- Is an Important Medical Event;

NOTE: Medical and scientific judgement should be exercised in deciding whether expedited reporting is appropriate in other situations, such as important medical events that may not be immediately life-threatening or result in death or hospitalization but may jeopardize the patient or may require intervention to prevent one of the other outcomes listed in the definition above. These should also usually be considered serious.

8.5.2.2.13.2.3 Pregnancy

Any report of pregnancy recorded for any female patient or for a female partner of a male patient should be reported to the Sponsor within the same timelines as an SAE, i.e. immediately (without undue delay, under no circumstances later than 24 hours following the first awareness/ within 30 days of IMP administration), but a separate form should be used. Pregnancy should be followed up at least until the birth or abort.

8.5.2.2.13.2.4 SAE Onset and SAE Stop Dates

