The important risks such as multi-organ failure, hypersensitivity, adverse hemodynamic effects and cardiovascular effects will be documented as AEs and will be listed and tabulated by system organ class and preferred term (MedDRA) for treatment emergent adverse events. The number of events, as well as the number and rate of affected patients will be reported for each treatment group. Pre-treatment emergent adverse events will be listed only.

Vital signs

Vital signs include Systolic blood pressure, Diastolic blood pressure, Heart rate, Body temperature and Respiratory rate.

Basic statistics will be computed for absolute values and the absolute change from baseline.

Vital signs will be tested before and after each dose (within 30 min before/after IMP administration) and only once at the visits without IMP. Baseline is defined as Screening value. Daily mean values of assessments before/after IMP administration will be used for calculation of absolute change from baseline at visits with IMP administration.

Oxygen saturation (part of vital signs, but measured only once per visit)

Oxygen saturation will be presented using basic statistics of absolute values for all visits and change from baseline for all after baseline visits.

Clinical laboratory assessments

All continuous results of laboratory data will be converted to standard unit before any calculation if needed. Conversion of all lab values will be described in a separate document.

Value evaluation (Normal / Abnormal – CS / Abnormal – Not CS) will be summarized for all laboratory parameters using frequency table additionally.

Absolute values as well as absolute change from baseline for the following laboratory data will be analysed by visit using basic statistics:

- Biochemistry: AST (GOT), ALT (GPT), Alkaline Phosphatase (AP), Total bilirubin, Total protein, Uric acid, Potassium, Sodium, Albumin, Urea Nitrogen (BUN), Creatinine, eGFR

(assessment is calculated according to the formula used in local laboratory: CKD-EPI, Cockcroft-Gault or MDRD)

- Inflammatory indicators: C-reactive protein (CRP), ESR, Procalcitonin
- Myocardial enzymes: Creatine kinase (total), CKMB, LDH, [alpha] - hydroxybutyrate dehydrogenase ([alpha] -HBD), Troponin (cTnl), Blood lactic acid
- Hematology: Red blood cells (RBC), Hematocrit, White blood cells (WBC), Hemoglobin, Platelets
- Coagulation: Prothrombin time (PT), Activated partial thromboplastin time (APTT), D-dimer, FIB

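### Two different tests decide whether a laboratory change linked to COVID-19 is recorded as an adverse event, and SAP section 4.5 describes no patient-level laboratory count to cover the gap

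*Protocol*

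**What the plan says.** **Recording rule (Protocol 8.5.2.2.13.1.4).** The exemption reads "Changes in laboratory values that are clinically significant (cs) and are specific for COVID-19 do not need to be documented as adverse events (AE". The sentence after it reads "Clinically significant changes in laboratory values that are not due to COVID-19 need to be documented as AEs". The physician then decides "whether a change in a laboratory parameter is clinically significant and therefore represents an AE". The section gives no list of parameters, no threshold and no adjudication. The summary of changes for version 6.0 lists a clarification of this section, so the rule was put in on purpose.

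**General AE definition (Protocol 8.5.2.2.13.1).** "An AE can therefore be any unfavorable and unintended sign (including an abnormal laboratory finding", and this holds whether or not the finding is considered related to the product. AEs "are collected from the time of first dose administration, regardless of the relationship to the IMP".

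**Causality (Protocol 8.5.2.2.13.1.2).** Underlying and intercurrent disease is weighed when the investigator judges the relationship of an AE that already exists.

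**Serious events (Protocol 8.5.2.2.13.2.2).** "A SAE is any untoward medical occurrence (whether considered to be related to IMP or not", with no exemption for COVID-19.

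**Analysis (SAP 4.5).** The treatment-emergent, relatedness and important-risk tables are built from AE records. "The important risks such as multi-organ failure, hypersensitivity, adverse hemodynamic effects and cardiovascular effects will be documented as AEs". Separately, laboratory values and change from baseline are summarised by visit, each parameter gets a frequency table of normal, abnormal clinically significant (CS) and abnormal not CS, and all abnormal evaluations are listed. SAP section 4 tabulates the arms separately and puts unscheduled visits in listings only.

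**The concern.** The judgement that a change belongs to the disease is made before recording. A change set aside at that point never becomes an AE, so nobody records whether the drug could have caused it.

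The protocol itself gives investigators grounds to attribute organ changes to COVID-19. Section 6.7 links "lymphocytopenia and elevated alanine aminotransferase, d-dimer, creatine kinase, high-sensitivity cardiac troponin I, prothrombin time, and disease severity" to intensive care admission and raises possible direct cardiac involvement by the virus. Section 8.4.5 says that the virus can infect the kidneys.

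Some of the same organs carry concern for the drug. Section 6.7 reports that in the earlier ARDS study one of the events resulting in death, an acute renal failure, was considered related to study drug. SAP 4.5 names multi-organ failure and cardiovascular effects as important risks.

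At stake is how complete the AE comparison between arms is for non-serious organ effects that resemble the disease.

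**Working it through.** **1. The two sentences side by side.** Take a clinically significant laboratory change.

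| Change is | First sentence | Second sentence |
|---|---|---|
| specific for COVID-19 | need not be recorded | no duty stated |
| due to COVID-19 but not specific for it | not exempt | no duty stated |
| not due to COVID-19 | not exempt | must be recorded |

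The middle row is the problem. Creatinine, ALT, CK and troponin can rise for many reasons, so a rise in any of them will usually fall there if the physician attributes it to the disease. A site that follows the first sentence falls back on the general definition and can record it. A site that reads the second sentence as the whole duty can omit it.

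**2. What follows from omission.** No AE record means no relationship assessment, and no entry in the treatment-emergent or relatedness tables. The change reaches the important-risk table only if a separate clinical event is recorded.

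**3. What remains without an AE record.** Values and CS frequencies are shown by visit and arm, and abnormal values are listed. The DSMB receives laboratory data (Protocol section 10). A criterion on eGFR stands outside AE recording (Protocol 8.3.3.3).

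**4. Gaps in what remains.**
- SAP 4.5 describes frequencies by visit. It describes no count of patients who develop a new CS value at any time after baseline.
- Unscheduled results appear in listings only (SAP section 4).
- Table 1 schedules no laboratory tests on Days 4 and 6, and they need not be done if the Day 28 visit is by phone.
- Protocol 8.7.1.2.7 promises shift tables from baseline by normal range. SAP 4.5 does not mention them for laboratory data, and SAP section 5 lists no such change. They may be in SAP Appendix A, which is not available here.

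**5. Size, as an illustration only.** The documents give neither the rate of new CS changes nor the share that would go unrecorded. Assume true rates of 10% (placebo) and 25% (APN01), 100 patients per arm (Protocol 8.7.2), and the same unrecorded share f in both blinded arms.

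Recorded rate = true rate × (1 − f). Visible difference = (25 − 10) × (1 − f) = 15 × (1 − f) percentage points.

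The last column is the probability that a pooled two-proportion z test at two-sided 5% would flag the difference, by exact enumeration of both binomials.

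| f | Recorded, placebo vs APN01 | Difference (points) | Probability |
|---|---|---|---|
| 0% | 10.0% vs 25.0% | 15.0 | 0.816 |
| 10% | 9.0% vs 22.5% | 13.5 | 0.764 |
| 50% | 5.0% vs 12.5% | 7.5 | 0.483 |
| 80% | 2.0% vs 5.0% | 3.0 | 0.186 |
| 90% | 1.0% vs 2.5% | 1.5 | 0.095 |

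The risk ratio stays at 25/10 = 2.5 throughout. Protocol 8.7.1.2.7 plans no tests on AEs, so the last column only gauges how visible a difference would be. The laboratory tables do not change with f.

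**The case against.** The strongest reply is that the exemption is narrow. It covers only laboratory values, and only those specific for COVID-19, which on a literal reading is very little. The second sentence creates a duty to record and grants no exemption. Clinical diagnoses are untouched, serious events are reportable whatever their cause, and the earlier renal event, being fatal, would be a serious event here. The clause on relationship in the AE definition concerns relationship to the drug, so the passages are in tension but do not contradict each other outright.

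All of this stands, and it rules out three stronger readings:

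- **Drug-related organ injury is hidden from any comparison between arms.** A reader might infer this, but the documents do not support it. Laboratory values and CS frequencies are tabulated by arm whether or not an AE was recorded.
- **The important-risk table is defeated.** SAP 4.5 says that the named risks will be documented as AEs. Isolated renal or liver injury is not named there, so its absence from that table would not be due to the exemption alone.
- **Hypernatraemia shows the danger.** More such events were reported with APN01 (Protocol 6.6.6), but section 6.7 calls them mild and consistent with sodium levels on placebo.

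The reply does not remove the middle row of the first table, the lack of a causality record for an omitted change, or the gaps in the laboratory reporting. Serious-event reporting does not reach non-serious organ changes.

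**Conclusion.** The point holds in a limited form. The two sentences in Protocol 8.5.2.2.13.1.4 set different tests and sit uneasily with the AE definition in 8.5.2.2.13.1. Non-serious renal, hepatic or cardiac laboratory changes attributed to COVID-19 may therefore be missing from the AE records, and so from the treatment-emergent and relatedness tables. How often depends on how sites read the rule, which the documents do not show.

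The loss falls on the AE tables and the causality record; the laboratory data remain in the trial. The attenuation figures rest wholly on assumed rates, and on an unrecorded share assumed equal in both arms. The statement that no patient-level count or laboratory shift table is described applies to the SAP text, since Appendix A could not be checked. The point is worth acting on because the remedy is cheap and uses flags already collected.

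**What to change.** 1. **Protocol 8.5.2.2.13.1.4.** Reconcile the two sentences with each other and with 8.5.2.2.13.1, so that one test applies. Judge presumed cause at the causality step (8.5.2.2.13.1.2), not when deciding whether to record.
2. **SAP 4.5.** Add, by arm, the number and percentage of patients with any new post-baseline CS value, unscheduled results included, for creatinine/eGFR, ALT/AST/bilirubin, CK/troponin, sodium, potassium and platelets. Derive it from the existing CS flags, whether or not an AE was recorded. Define new as not CS at baseline. The flag still rests on the physician's view of clinical significance, but not on attributed cause.
3. **SAP 4.5 or Appendix A.** Include the baseline-to-visit laboratory shift tables promised in Protocol 8.7.1.2.7 if Appendix A lacks them, or list their removal in SAP section 5.

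The cost is a wording change, a few extra tables and possibly more AE entries in both arms. Items 2 and 3 need no new data and also cover patients enrolled under the present wording. Requiring an AE entry for every organ-related change, with a new eCRF field for attribution, would go further, but that burden on sites is debatable and is not needed to obtain the comparison in item 2.
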